### Prophylactic treatment

The suggested dose for prophylactic treatment in patients  $\geq$  12 years of age is 50 IU/kg twice weekly, ranging from 40-60 IU/kg, which may be increased to 75 IU/kg, if applicable. In the BAX326 pivotal study, the suggested standard prophylactic dose regimen for subjects  $\geq$  12 years of age was confirmed, as the median dose was 50.5 IU/kg ranging from 40 to 63 IU/kg (mean  $49.5 \pm 4.8$  IU/kg).

For pediatric patients the suggested dose is 50 IU/kg twice weekly, ranging from 40-80 IU/kg, with dose and dosing frequency adjustments depending on the individual recovery and clinical response. The suggested dose is based on studies performed with BeneFIX in pediatric PTPs as well as in PUPs.

In a multicenter study performed by Monahan et al., 25 patients, aged < 6 years with severe hemophilia B, regardless of previous treatment, received BeneFIX for the treatment of bleeding episodes and/or prophylaxis (intermittent, routine, and/or surgery related) over 6 to 12 months. Of the 25 subjects, 22 received routine prophylaxis once (n = 9) or twice (n = 12) weekly. One subject received 1-2 infusions per week. The median dose for routine prophylaxis and intermittent infusions was 57.6 IU/kg rFIX, ranging from 27.9 to 187.2 IU/kg. The mean dose was  $64.6 \pm 22.3$  IU/kg. Investigator-prescribed routine prophylaxis included once weekly infusions with doses ranging from 42 to 105 IU/kg (n = 9), 1-2 infusions per week with a dose of 100 IU/kg (n = 1). Most patients (n = 12) had twice weekly infusions with doses ranging from 33 to 87 IU/kg. Near complete prevention of spontaneous breakthrough hemorrhages (< 1 per year) was obtained after routine prophylaxis with 1 or 2 rFIX infusions per week. In a study performed by Shapiro et al. in 63 PUPs with severe or moderately severe hemophilia B < 1 month to 14 years of age, 42 patients received rFIX for routine or intermittent prophylaxis. The median dose was 60.60 IU/kg, ranging from 9.70 to 230.40 IU/kg, and a mean of  $71.57 \pm 36.89$  IU/kg. Of the 32 patients who were on routine prophylaxis, 24 received rFIX  $\geq 2$  times per week with a mean dose of  $72.5 \pm 37.1$  IU/kg. The remaining 8 patients received rFIX once weekly with a mean dose of  $75.9 \pm 17.9$  IU/kg. The percentage of patients who had early spontaneous breakthrough bleeds was lower in those who received 2 or more infusions per week (3 of 24; 13%) compared with those receiving 1 infusion per week (2 of 8 patients: 25%). In addition, hemostatic efficacy and safety of a PK-tailored treatment regimen, which is based on the subject's individual PK, will be evaluated in this study. The target is to maintain FIX activity levels in plasma of at least 1% above the subject's individual FIX level observed at baseline, ie, at screening of the parent study or, in case of newly recruited subjects, at screening of this study. It is expected that the most common frequency will be twice weekly. The dose is not to exceed 100 IU/kg.

Patients with moderate hemophilia, ie, FVIII or FIX levels between 1-5%, have fewer hemarthroses, usually trauma-induced, and a decreased likelihood of developing arthropathy than patients with severe hemophilia with FVIII/FIX activity levels < 1%. This observation led to the use of prophylactic infusions to convert a patient from a severe to a moderate bleeding phenotype. Although FVIII or FIX activity levels of 1% are generally considered as protective levels and help identify clear targets, it does not necessarily mean that these levels are the correct baseline level for an individual patient. In a pooled analysis of 143 pediatric and adult patients who had received Advate, a clear correlation between increased total bleeds and hemarthrosis and time spent with a FVIII activity level < 1% could be demonstrated.

Further analyses revealed that half-life and dose frequency had a larger impact on FVIII trough levels and time spent with a FVIII level below 1% per week than incremental recovery or the infused dose/kg. It is expected that these findings also apply to subjects with severe or moderately severe hemophilia B.

The approach of a PK-tailored prophylactic dosing regimen takes the generally observed marked inter-patient variability of pharmacokinetic parameters into account since dose and frequency will be based on the subject's individual PK. It is expected that by ensuring a FIX level of at least 1% above baseline the frequency of bleeding episodes may be substantially reduced.

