### 8.6.3.1 Prophylactic Treatment

The prophylactic treatment regimen with BAX326 will be at the discretion of the investigator and will consist of one of the following treatment options:

- Standard prophylaxis with twice weekly prophylactic infusions of 50 IU/kg (range of 40-60 IU/kg, which may be increased to 75 IU/kg, in subjects  $\geq$  12 years of age; range of 40-80 IU/kg in pediatric subjects  $<$  12 years), or
- modified prophylaxis determined by the investigator. The dose can be increased up to 100 IU/kg, if applicable; or
- PK-tailored prophylaxis based on subject's individual PK. The maximum dose is 120 IU/kg.

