**Please note:**

*The dose and dosing frequency should be adjusted according to the individual subject's age, the number of breakthrough bleeds and/or the subject's physical activity.*

*It is recommended to administer prophylactic infusions prior to weekdays with increased physical activity.*

*In subjects with severe hemophilic arthropathy and/or target joints who continue experiencing recurrent bleeding episodes despite adjustments of the prophylactic dose and/or dosing frequency, an ultrasound of the affected joint(s) should be performed to verify the presence of a bleed.*

Dose and/or frequency adjustments should be performed if a subject meets either of the following criteria:

- **Two or more spontaneous** (not related to trauma) bleeding episodes in the same target joint within any 3-month period, **OR**
- **One or more spontaneous** (not related to trauma) bleeding episodes in a non-target joint or a non-joint within any 3-month period

In such a case, the dose and/or frequency will be increased. The dose is not to exceed 100 IU/kg and an increase in frequency should be considered. It is recommended to consult the sponsor.

The regimen should preferably be maintained until the end of the study, unless clinical circumstances or the subject's wish necessitate a change as described above. Any change in the regimen, and the reason for such change, will be recorded in the eCRFs.

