### 8.6.3.1.1 PK-Tailored Prophylaxis

Subjects receiving PK-tailored prophylactic treatment who have not participated in a PK study either in the BAX326 pivotal or BAX326 surgery study will undergo an abbreviated PK study with 1 pre- and 5 post-infusion sampling timepoints up to 72 hours following the infusion of  $75 \pm 5$  IU/kg of BAX326. Only 500 IU potency vials from one lot may be used for the PK study in individual subjects. The actual vial potency will be used to calculate the total units administered and rounded up or down to the nearest whole vial. In subjects < 12 years of age, the total calculated dose may not be rounded up or down to the nearest whole vial. There must be a minimum wash-out period of 5 days, preferably 7 days, prior to the PK infusion and the subject must be in a non-bleeding state. Based on the subject's individual PK, the dose will be calculated to ensure that FIX activity levels in plasma of at least 1% above the subject's individual FIX level observed at baseline are maintained. The maximum dose is 120 IU/kg. Doses higher than 120 IU/kg are not allowed and therefore frequencies requiring a higher dose are excluded. Subjects continuing from the continuation study and newly recruited subjects with confirmed eligibility will receive BAX326 at a dose regimen as determined by the investigator until the dose and frequency, calculated by the sponsor, are available at the study site. Bleeding episodes will also be treated with BAX326.

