**Table 21.1-1**  
**Flow Diagram of Required Procedures for Baxalta Clinical Study 251001**

**APPLICABLE TO ALL PROPHYLACTIC REGIMENS THROUGHOUT**  
**THE STUDY:**

Dose and/or frequency adjustments should be performed if a subject meets either of the following criteria:

- **Two or more spontaneous** (not related to trauma) bleeding episodes in the same target joint within any 3-month period, **OR**
- **One or more spontaneous** (not related to trauma) bleeding episodes in a non-target joint or a non-joint within any 3-month period

In such a case, the dose and/or frequency will be increased. It is recommended to consult the sponsor.

**In subjects with severe hemophilic arthropathy and/or target joints who continue experiencing recurrent bleeding episodes despite adjustments of the prophylactic dose and/or dosing frequency, an ultrasound of the affected joint(s) should be performed to verify the presence of a bleed.**

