9.1 IR Over Time

Analysis of IR over time will be carried out on the FAS.

IR_{30min} in IU/dL/IU/kg will be calculated as:

$$\text{IR}_{30\text{min}} = \frac{C_{30\text{min}}[\text{IU/dL}] - C_{\text{pre-infusion}}[\text{IU/dL}]}{\text{dose per kg body weight [IU/kg]}}$$

where C_{30min} and C_{pre-infusion} relate to the unadjusted concentration values.

IR_{30min} of FIX will be summarized for baseline and end of study using descriptive statistics. Also the change from baseline to end of study will be described using summary statistics.

These tables will be created for the on-demand treatment only (i.e. subjects who received on-demand treatment exclusively over the whole study period), for the overall prophylaxis (combined standard, modified and PK-tailored prophylaxis) only, for subjects who received on-demand treatment and any prophylaxis treatment (i.e. subjects who switched during the study) as well as for all treatment regimens together.

In addition, IR_{30min} of FIX will be provided in a by-subject listing.

The maximum allowable dose is 120 IU/kg – all cases with a dosage higher than 120 IU/kg will be excluded from the IR tables and will be only displayed in a listing.

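### The protocol gives both 100 and 120 IU/kg as the dose ceiling for PK-tailored prophylaxis, and its breakthrough-bleed adjustment rule does not say whether its 100 IU/kg cap covers that regimen

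*Protocol*

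**What the plan says.** Section 6.1 of the protocol, under Prophylactic treatment, introduces the regimen by saying that the "hemostatic efficacy and safety of a PK-tailored treatment regimen, which is based on the subject's individual PK, will be evaluated in this study". It gives the trough target and the dosing frequency expected to be most common (twice weekly), and closes: "The dose is not to exceed 100 IU/kg".

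Section 8.6.3.1 lists the prophylactic options, among them "PK-tailored prophylaxis based on subject's individual PK. The maximum dose is 120 IU/kg". The same list gives modified prophylaxis its own limit of 100 IU/kg. Further down, the section sets criteria for raising dose or frequency after spontaneous bleeds and adds: "The dose is not to exceed 100 IU/kg and an increase in frequency should be considered". It names no regimen there and makes no exception.

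Section 8.6.3.1.1, which is devoted to PK-tailored prophylaxis, says: "Doses higher than 120 IU/kg are not allowed and therefore frequencies requiring a higher dose are excluded". Section 8.1.3 says the same.

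The flow diagram in Table 21.1-1 repeats the adjustment criteria under a banner beginning "APPLICABLE TO ALL PROPHYLACTIC REGIMENS THROUGHOUT", but states no dose cap with them.

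The SAP uses 120 IU/kg for PK-tailored prophylaxis in its design summary (2.1 and 2.2) and in the compliance measures (6.6). In 9.1 it says "The maximum allowable dose is 120 IU/kg" and removes higher doses from the incremental recovery tables.

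**The concern.** A ceiling on dose is a rule that sites, monitors and the analysis must all read in the same way. Here one regimen has two ceilings within a single protocol, and one of the conflicting statements sits in the operative treatment section.

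Two things are at stake. The first is conduct: someone adjusting a PK-tailored subject after breakthrough bleeds is referred to a section that gives both figures. The second is reporting: SAP 6.6 measures compliance against the dose limit, and SAP 6.7 summarizes protocol deviations. A dose of 110 IU/kg meets the SAP compliance limit, yet whether it departs from the protocol depends on which section is consulted.

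**Working it through.** The plan has no figure to reproduce on this point, so the check is a reconciliation of every statement of the ceiling.

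| Place | What it covers | Limit (IU/kg) |
|---|---|---|
| Protocol 6.1 | PK-tailored | 100 |
| Protocol synopsis, 8.1.1, 8.1.2, 8.1.3 | PK-tailored | 120 |
| Protocol 8.6.3.1, regimen list | PK-tailored | 120 |
| Protocol 8.6.3.1, regimen list | Modified | 100 |
| Protocol 8.6.3.1, adjustment rule | Increases after breakthrough bleeds; no regimen named | 100 |
| Protocol 8.6.3.1.1 | PK-tailored | 120 |
| Protocol 14.3.2.2 | Maximum dose, in the PK analysis text | 120 |
| Protocol Table 21.1-1 | Same adjustment criteria, all prophylactic regimens | none stated |
| SAP 2.1, 2.2, 6.6 | PK-tailored | 120 |
| SAP 9.1 | Incremental recovery tables | 120 |

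**Does the 6.1 limit concern PK-tailored dosing?** Yes. It closes the text on that regimen, directly after the regimen's expected frequency. Modified prophylaxis is not the subject there.

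**Does the adjustment rule reach PK-tailored subjects?** Footnote q of Table 21.2-1 and footnote m of Table 21.2-2 require the regimen to be re-evaluated in standard, modified and PK-tailored subjects alike, and refer to section 8.6.3.1 for guidance. The adjustment guidance therefore reaches them. Whether the 100 IU/kg cap comes with it is not stated.

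**Which doses are in conflict?** Testing example doses against each limit:

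- 100 IU/kg passes both.
- 105, 110 and 120 IU/kg fail the 100 limit and pass the 120 limit.
- 121 IU/kg fails both.

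The conflict covers doses above 100 and up to 120 IU/kg.

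**Can a PK-tailored dose fall in that band?** As an illustration only, assume a single dose, mono-exponential decline and a trough 1 IU/dL above baseline. Then dose D = 2^(τ/T) / IR, where τ is the dosing interval, T the half-life and IR the incremental recovery. Solving for half-life gives T = τ / log2(D × IR).

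- Pivotal median IR 0.88 (section 6.4.1), τ = 168 h. D = 100: 168 / log2(88) = 26.0 h. D = 120: 168 / log2(105.6) = 25.0 h.
- Lowest pivotal IR 0.53, τ = 96 h. D = 100: 96 / log2(53) = 16.8 h. D = 120: 96 / log2(63.6) = 16.0 h.

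The 168 h interval matches the 6 to 8 day spacing that SAP 6.6 checks for PK-tailored infusions. The 96 h interval is the longer gap in twice-weekly dosing (Table 11.1-4). Both half-life bands lie within the pivotal range of 15.83 to 52.34 h in section 6.4.1, so the band can be reached. Each is narrow, about 1.0 h and 0.7 h wide. At the pivotal median half-life of 24.58 h and IR of 0.88, the formula gives 129.7 IU/kg at 168 h (above both limits) and 17.0 IU/kg at 96 h (below both).

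**Where does the limit enter the analysis?** It enters the dose-limit measure in SAP 6.6 and the combined dose-limit and prescribed-dose measure there. It also enters the exclusion in SAP 9.1, because Table 11.1-3 of the protocol lets recovery infusions use the tailored dose when that is the higher. It does not enter the primary outcome (SAP 8.1), the annualized bleeding rate (SAP 7.2.2) or membership of the Full Analysis Set (SAP 4.1).

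**The case against.** Section 6.1 is background, and the sections that set out the regimen agree with each other. The sponsor works out the initial PK-tailored dose and frequency, so a site does not choose a ceiling at the start, and consulting the sponsor is recommended at adjustment. The 100 IU/kg cap in the adjustment rule can be read as limiting escalation led by the investigator, with PK-tailored doses governed by 8.6.3.1.1. The cap equals the modified-prophylaxis limit and exceeds the standard limits of 75 and 80 IU/kg, so it is not simply each regimen's own ceiling restated.

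Much of this stands. It makes divergent starting doses unlikely and leaves the reach of the adjustment cap ambiguous rather than settled. It does not remove the conflict in 6.1, which is worded as a requirement, nor does it supply the missing exception in 8.6.3.1.

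Several stronger readings are tempting but not supported:

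- A reader might take 8.6.3.1 as a section that sets 100 IU/kg. It gives both figures.
- A reader might take Table 21.1-1 as extending the 100 IU/kg cap to every regimen. It extends the adjustment criteria and leaves the cap out.
- A reader might infer that the SAP is wrong. It uses 120 IU/kg throughout, in line with protocol 14.3.2.2.
- A reader might infer that deviations cannot be classified consistently. SAP 6.7 gives no dose-based rule, so an effect on deviation counts is possible but not shown.

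**Conclusion.** The protocol contradicts itself on the PK-tailored ceiling: 100 IU/kg in 6.1 against 120 IU/kg in the sections that set out the regimen. Section 8.6.3.1 adds a second, narrower fault, a 100 IU/kg adjustment cap with unclear scope beside a 120 IU/kg regimen limit. This is an internal inconsistency and is wrong as written.

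It affects doses above 100 and up to 120 IU/kg. The number of subjects or infusions in that band is not in the documents. The half-life illustration shows only that the band can be reached under a simple single-dose model, not that any subject was dosed there.

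The consequence is for clarity of dosing, for the descriptive compliance ratios, and possibly for deviation counts and the recovery-table exclusion. A reader might infer damage to the main safety or bleeding-rate results, but the ceiling plays no part in how either is defined. That most passages say 120 IU/kg does not settle which limit is right, and no view is taken here.

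**What to change.** The sponsor's clinical team should reconcile section 6.1 and the adjustment rule in 8.6.3.1 with 8.1.3, the 8.6.3.1 regimen list, 8.6.3.1.1, 14.3.2.2 and Table 21.1-1, so that each regimen has one ceiling. The text should say whether the adjustment cap covers PK-tailored subjects, and the flow diagram should carry the same statement.

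SAP 6.6, and 9.1 if affected, should change only if the reconciled PK-tailored limit differs from 120 IU/kg or if a separate limit applies after adjustment. Otherwise the SAP can stand.

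The cost is protocol wording and, at most, a revised threshold in descriptive tables. No new data are needed.

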## 6.2 Clinical Condition/Indication

Hemophilia B is an X-linked recessive, congenital bleeding disorder caused by deficient or defective coagulation FIX. Its prevalence is approximately 20% of that of hemophilia A with an incidence of 1 in 30,000 live male births. The severity of both hemophilia A and B is classified according to plasma procoagulant levels, with levels < 1% of normal defined as severe, between 1% and 5% classified as moderate, and > 5% to < 40% defined as mild. Approximately 30 to 45% of persons affected have severe hemophilia B. Plasma-derived and, more recently, recombinant FIX products have been successfully used both prophylactically and to treat bleeding episodes.

There are differences in the severity of the clinical phenotype of patients with hemophilia A and B. The phenotype often does not always reflect the measured procoagulant concentrations in plasma. Hemophilia B patients tend to bleed less, undergo fewer arthroplasties, and require less intense prophylaxis than hemophilia A patients with similar plasma concentrations of the respective factor. Schulman et al devised a Hemophilia Severity Score consisting of annual incidence of joint bleeds, the WFH Orthopedic joint score, and the annual consumption of factor of adult patients with hemophilia A and B at their hospital in Sweden. The median score was higher in patients with severe hemophilia A than severe hemophilia B (median 0.50 versus 0.29), indicating more severe disease in hemophilia A patients. Pai et al investigated the frequency of bleeding and clotting factor use in hemophilia A and B patients: patients with hemophilia B had 35% fewer bleeds than hemophilia A patients, but concentrate use per bleed was similar. In a survey of 2663 hemophilia patients in Canada by Biss et al, 23% of hemophilia A patients and 11% of hemophilia B patients received prophylaxis (ie., a concentrate infusion at least once a week for  $\geq 45$  weeks of the year). Tagariello et al. found that patients in Italy with hemophilia A had a 3-fold higher risk of undergoing joint arthroplasty than patients with hemophilia B.

The most serious complication of the disease is the development of inhibitory antibodies that neutralize the coagulatory activity of the infused factor concentrate; this occurs in 1.5 to 3% of patients with hemophilia B. Inhibitor development is more common in patients with hemophilia A, with about 30% of patients with severe hemophilia A developing inhibitors. As inhibitor development is relatively rare in hemophilia B there is sparse data on risk factors or the immunological processes involved. An increased incidence of inhibitor development has been seen in patients with certain genetic mutations: those with complete deletions or rearrangements have a higher risk of developing inhibitors than those with nonsense or frame-shift mutations. Furthermore, more patients with hemophilia B than with hemophilia A have been found to be cross-reacting material positive (CRM+) on the basis of detectable FIX antigen. Since fewer CRM+ than CRM- individuals with hemophilia B develop inhibitors, it is further postulated that patients with detectable FIX polypeptide (CRM+) develop tolerance to the 'self' protein that may extend to the exogenous FIX found in replacement therapy.

Inhibitors reduce the IR and half-life of FIX, resulting in relative or complete refractoriness to replacement therapy. Although inhibitory alloantibodies to FIX are far less frequently encountered in patients with hemophilia B than those to FVIII in hemophilia A, their onset may be complicated by anaphylaxis if hemophilia B patients are re-exposed to FIX. The risk of developing inhibitors to FIX is highest after relatively few (10 to 20) exposure days (EDs) to FIX. Often, the allergic reactions occur before inhibitory antibodies are detected. Allergic reactions include pruritus, urticaria, erythema, or angioedema without respiratory or cardiovascular compromise; anaphylactoid syndromes include the above symptoms with respiratory or cardiovascular compromise.

High titer inhibitors require a bypass treatment such as activated prothrombin complex concentrates or activated recombinant factor VII, or temporary removal of the antibody using plasmapheresis or immunoadsorption. An alternative approach is to induce immune tolerance by giving large doses of FIX regularly over several months. However, there are issues with lack of response in patients with an allergic phenotype and the development of nephrotic syndrome following immune tolerance induction (ITI).

The International Society of Thrombosis and Haemostasis-Scientific and Standardization Committee international FIX inhibitor registry was established in 1997 to collect data on the occurrence of inhibitors and the complications associated with them.

Between 1997 and 2006 data from 94 patients were recorded with anaphylaxis reported in 56 of them, and severe allergic reactions in 38. Of 39 patients who underwent some form of ITI only 5 were cleared of inhibitor. Nephrotic syndrome developed in 13 patients 8 to 9 months into the ITI regimen; the patients presented with periorbital edema, proteinuria and hypoalbuminemia. Eleven of the 13 patients had a history of anaphylaxis.

